14.3 Vital Signs

Vital signs are assessed at Baseline, Weeks 2, 4, 8, 12, 16, 28, 40, and 52 (EOT/ET).

Vital signs including weight, height (measured at the screening visit of antecedent studies), and the derived BMI will be summarized using descriptive statistics at Baseline and all scheduled post-Baseline visits. The change from Baseline values will also be summarized at the scheduled post-Baseline visits.

Vital sign values will be considered PCI if they meet the criteria listed in [Table 4](#). The number and percentage of subjects with post-Baseline vital signs that are PCI will be summarized at scheduled post-Baseline visits and for overall post-Baseline. For the overall post-Baseline summaries, all post-Baseline values will be considered, including unscheduled and out of window values. Subjects with multiple PCI values for a given parameter will be counted only once for that parameter. For the by-visit summary, the numerator for the percentage is the number of subjects with a post-Baseline PCI value for the given parameter and visit, and the denominator is the number of subjects with non-missing values for the given parameter and visit. For the overall post-Baseline summary, the numerator for the percentage is the number of subjects with at least 1 post-Baseline PCI value for the given parameter, and the denominator is the number of subjects with at least 1 post-Baseline value

for the given parameter. A listing of all PCI values in study ACP-103-055 will be provided. This listing will include all observations from study ACP-103-055 for those subjects and parameters for which at least one PCI value (including Baseline) was observed.

Table 4 Criteria for Potentially Clinically Important Vital Signs

Vital Sign Parameter	Unit	Criteria ^a		
		Observed Value	And/Or	Change Relative to Baseline
Systolic blood pressure (supine or sitting)	mmHg	≥180	And	Increase of ≥20
		≤90	And	Decrease of ≥20
Diastolic blood pressure (supine or sitting)	mmHg	≥105	And	Increase of ≥15
		≤50	And	Decrease of ≥15
Pulse (supine or sitting)	bpm	≥120	And	Increase of ≥15
		≤50	And	Decrease of ≥15
Weight	kg	Not Applicable		Increase of ≥7%
				Decrease of ≥7%

^a A post-baseline value is considered as a PCI value if it meets both criteria for observed value and change from baseline.

14.4 Electrocardiogram (ECG)

All tracings will be evaluated by qualified clinicians. At the Baseline visit, the machine-read results will also be recorded. All data, including the machine-read Baseline results, will be listed.

Observed values of ECG variables (heart rate, PR interval, RR interval, QRS interval, QT interval, and QTc intervals) and the changes from Baseline at scheduled visits will be summarized.

QTc intervals include QTcB (Bazett’s formula) and QTcF (Fridericia’s formula). QTcF will also be categorized into the following categories (msec) and the number and percentage of subjects in each category will be summarized at scheduled visits and overall post-baseline maximum:

- Observed: ≤450, 451 - ≤480, 481 - ≤500, and >500; >450; >480.
- Change from Baseline: ≤10, 11 - 30, 31 - 60, and >60; >30.

The above summaries will also be presented for the following subgroups: subjects with background antidepressant of citalopram, subjects with background antidepressant of escitalopram, and subjects with background antidepressant of venlafaxine.

For cardiologist’s interpretations, the number and percentage of subjects with ECG results

that are determined as normal or abnormal will be summarized at scheduled visits. The overall post-baseline worst interpretation will also be summarized (i.e. if a subject has one or more ECG results that is/are considered as abnormal, this subject will be counted in the abnormal category). Cardiologist’s interpretations will also be summarized in a shift table to determine the number and percentage of subjects with ECG results classified as normal or abnormal at scheduled post-Baseline visits relative to the same classification at the Baseline visit. The shifts from Baseline to overall post-Baseline worst interpretation will also be presented. For the by-visit shift summary, the denominator is the number of subjects with non-missing cardiologist’s interpretation at Baseline and the given visit. For the summaries of shift from Baseline to the overall post-Baseline worst interpretation, the denominator is the number of subjects with non-missing Baseline and at least 1 post-Baseline cardiologist’s interpretation.

Electrocardiogram values will be considered PCI if they meet or exceed the upper limit values listed in Table 5. The number and percentage of subjects with PCI values will be summarized at scheduled post-Baseline visits and for overall post-Baseline. For the by-visit summary, the numerator for the percentage is the number of subjects with a post-Baseline PCI value for the given parameter and visit, and the denominator is the number of subjects with non-missing values for the given parameter and visit. For the overall post-Baseline summary, the numerator for the percentage is the number of subjects with at least 1 post-Baseline PCI value for the given parameter, and the denominator is the number of subjects with at least 1 post-Baseline value for the given parameter. A listing of all PCI values in study ACP-103-055 will be provided. This listing will include all observations from study ACP-103-055 for those subjects and parameters for which at least one PCI value (including OL Baseline) was observed.

Table 5 Criteria for Potentially Clinically Important ECG Values

ECG Parameter	Unit	High PCI Criteria
QRS Interval	msec	≥120
PR Interval	msec	≥220
QTcB or QTcF	msec	>500
QTcB or QTcF: change from baseline	msec	>60

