### **9.5.3.2 Electrocardiograms**

ECG parameters, including changes from Baseline, will be summarized by timepoint using descriptive statistics. Additionally, categorical analyses will be conducted on the incidence of subjects with prolonged QTc intervals and changes in QTc intervals in accordance with ICH guidelines and Food and Drug Administration (FDA) E14 guidance document.

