5.1 General Data Reporting Conventions

For continuous variables, the following summary statistics will be provided: number of subjects, mean, standard error of the mean (SE), standard deviation (SD), minimum, maximum, and median. Unless specified otherwise, means, and medians will be presented to one more decimal place than the raw data, and the SDs and SEs will be presented to 2 more decimal places than the raw data.

For categorical variables, summaries will include the number and percentage of subjects in each category, using the number of subjects with non-missing values as the denominator for the percentages (unless otherwise specified). Categories with zero counts will not have zero percentages displayed. Percentages will be presented to 1 decimal place.

When converting number of days to months, it will be calculated as the number of days divided by 365.25 and then multiplied by 12. When converting number of days to years, it will be calculated as the number of days divided by 365.25.

No hypothesis testing is planned. Descriptive summaries of all safety and efficacy endpoints will be provided.

All safety and efficacy endpoints will be summarized for the Safety Analysis Set. In addition, summaries by treatment group according to the original double-blinded treatment actually received in the antecedent study (placebo or pimavanserin) will also be provided.

For each continuous measure in safety and efficacy analyses, change from Baseline results will be presented in two ways:

1. Main analysis: using the Baseline from Study ACP-103-055 and reporting the changes across Study ACP-103-055 timepoints
2. Exploratory analysis: using the Baseline from the antecedent study (ACP-103-054 or ACP-103-059), and reporting the changes across Study ACP-103-055 timepoints

For the treatment responder rate, the summary will also be presented in two ways:

1. Main analysis: using the Baseline from Study ACP-103-055 and reporting the rate across Study ACP-103-055 timepoints
2. Exploratory analysis: using the Baseline from the antecedent study (ACP-103-054 or ACP-103-059), and reporting the rate across Study ACP-103-055 timepoints

The treatment remission rate and the percentage of subjects with sexual dysfunction will also be summarized across Study ACP-103-055 timepoints using the Baseline from Study ACP-103-055 and the Baseline from the antecedent double-blind studies as reference points.

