14 SAFETY ANALYSES

The safety summaries will be presented for the Safety Analysis Set using descriptive statistics. Safety variables include AEs, clinical laboratory variables, vital signs, body weight, BMI, physical examinations, ECG, C-SSRS, ESRS-A, and sexual dysfunction defined as a CSFQ-14 total score of ≤ 47 for men and ≤ 41 for women. Safety variables will also be summarized by the double-blind treatment group in the antecedent studies. For each continuous measure in clinical laboratory variables, vital signs, and electrocardiogram, change from Baseline results will be presented in two ways (main analysis and exploratory analysis) as specified in Section 5.1.

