Sodium	mEq/L	≤125	≥155	mmol/L	≤125	≥155
Potassium	mEq/L	≤3.0	≥5.5	mmol/L	≤3.0	≥5.5
Calcium, total	mg/dL	<8.0	>11.0	mmol/L	<2.0	>2.75
Lactate Dehydrogenase (LDH)	U/L	No lower limit	≥3 X ULN	U/L	No lower limit	≥3 X ULN
Alkaline Phosphatase	U/L	No lower limit	≥3 X ULN	U/L	No lower limit	≥3 X ULN
Uric acid (male)	mg/dL	No lower limit	≥10.5	umol/L	No lower limit	≥624.75
Uric acid (female)	mg/dL	No lower limit	≥8.5	umol/L	No lower limit	≥505.75
Albumin	g/dL	≤2.6	≥6.0	g/L	≤26	≥60
Total Protein	g/dL	≤5.0	≥10.0	g/L	≤50	≥100
Chloride	mEq/L	≤85	≥120	mmol/L	≤85	≥120
Glucose (random)	mg/dL	≤45.1	≥200.0	mmol/L	≤2.48	≥11
Serum Creatinine	mg/dL	Not Applicable	>1.5 ULN	umol/L	Not Applicable	>1.5 ULN
Triglycerides	mg/dL	Not Applicable	>300	mmol/L	Not Applicable	>3.39
Gamma-Glutamyl Transferase (GGT)	U/L	Not Applicable	≥3 ULN	U/L	Not Applicable	≥3 ULN

Table 3 Criteria for Potentially Clinically Important Laboratory Values - Urinalysis

Urinalysis (qualitative dipstick)	Low PCI Criteria	High PCI Criteria
Blood (occult blood)	Not Applicable	≥ Moderate
Protein	Not Applicable	≥ 100 mg/dL
Glucose	Not Applicable	≥ 500 mg/dL

The number and percentage of subjects with the shift from baseline, both double-blind and open-label, to weeks 12 and 52 that meet the following criteria in the blood lipid parameters and glucose will be summarized by fasting status (fasting vs. non-fasting):

- Total Cholesterol – (<200 mg/dL to ≥240 mg/dL)
- Triglycerides – (<150 mg/dL to ≥200 mg/dL)
- LDL Cholesterol – (<100 mg/dL to ≥160 mg/dL)
- HDL Cholesterol – (≥40 mg/dL to <40 mg/dL)
- Glucose fasting – (<100 mg/dL to ≥126 mg/dL)
- Glucose non-fasting – (<140 mg/dL to ≥140 mg/dL)
- Glucose fasting – (≥100 mg/dL and <126 mg/dL to ≥126 mg/dL)
- Glucose non-fasting - (≥140mg/dL and <200 mg/dL to ≥200 mg/dL)

The pregnancy results (positive or negative) for female subjects will be presented in a listing.

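### Does SAP 14.4 need to say that the QTcF change categories are also counted from the antecedent double-blind Baseline?

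*SAP*

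**What the plan says.** SAP 14.4 has two QTcF groupings, one of observed values and one of change: "Change from Baseline: ≤10, 11 - 30, 31 - 60, and >60; >30". For both, "the number and percentage of subjects in each category will be summarized at scheduled visits and overall post-baseline maximum". Table 5 adds a potentially clinically important criterion of a QTc change above 60 msec. Neither place says which Baseline the change is taken from.

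The SAP works with two. Under SAP 5.1 the main analysis uses the open-label Baseline and an exploratory analysis uses the Baseline of the antecedent study. The opening paragraph of SAP Section 14 applies this to ECG: "For each continuous measure in clinical laboratory variables, vital signs, and electrocardiogram, change from Baseline results will be presented in two ways". The same paragraph calls for safety summaries by antecedent treatment group.

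Some counts and rates have their own two-Baseline sentence. In SAP 5.1: "For the treatment responder rate, the summary will also be presented in two ways". In SAP 14.2 the lipid and glucose criteria are to be summarised "with the shift from baseline, both double-blind and open-label, to weeks 12 and 52".

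Protocol 3.1 makes the antecedent end-of-treatment visit the Baseline of this study. Protocol 1.3 puts the drug's average QT prolongation at about 5-8 ms.

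**The concern.** The two-Baseline rule is worded for continuous measures, and a table of counts in bands is not obviously one. Three features of the text suggest that the categories fall outside it.

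- SAP 5.1 sets out a separate convention, "For categorical variables, summaries will include the number and percentage of subjects in each category", and SAP 14.4 describes the QTcF groupings in nearly the same terms.
- Protocol 9.5.3.2 adds the groupings to the descriptive change summaries: "Additionally, categorical analyses will be conducted on the incidence of subjects with prolonged QTc intervals and changes in QTc intervals".
- Responder rate is a categorised change, and it still has its own instruction. The QTcF change categories have none.

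If only the open-label Baseline were used, the prior-pimavanserin column would show only further change during the extension. Take a hypothetical subject with QTcF of 380 ms before drug, 400 ms at the end of the antecedent study and 415 ms in the extension. The rise on drug is 415 - 380 = 35 ms. The table would record 415 - 400 = 15 ms, and the observed value would stay in the lowest category. Safety is the primary objective and QT prolongation is an acknowledged effect of the drug, so a low count in the above-30 ms row could be misread. The same would hold for the citalopram, escitalopram and venlafaxine subgroups, for which SAP 14.4 repeats these summaries.

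**Working it through.** The plan states no figure on this point, so there is none to reproduce. The check has three parts.

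**1. Is the open-label Baseline on drug?** Protocol 3.1 gives total exposure of up to 58 weeks against 52 in this study: 58 - 52 = 6 weeks of possible earlier pimavanserin. The first open-label dose is taken the day after the Baseline visit, and no washout is described. For prior-pimavanserin subjects the answer is yes. For prior-placebo subjects it is no.

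**2. How much could the choice of Baseline move the counts?** Inputs from the documents: a shift m of 5 to 8 ms (Protocol 1.3). The Phase 2 study agrees: 7.2 - (-0.8) = 8.0 ms in Stage 2 (Protocol 1.1). Assumptions not in the documents: SD of change s between 10 and 20 ms, normal distribution, and a shift already complete at the open-label Baseline and stable afterwards. Then P(change > t) = 1 - Φ((t - m)/s), with m = 0 from the on-drug Baseline and m = 5 or 8 from the pre-drug Baseline. For t = 30 ms, one visit, prior-pimavanserin subjects:

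| s (ms) | m = 0 | m = 5 | m = 8 | Gap (points) |
|---|---|---|---|---|
| 10 | 0.14% | 0.62% | 1.39% | 0.49 to 1.26 |
| 12 | 0.62% | 1.86% | 3.34% | 1.24 to 2.72 |
| 15 | 2.28% | 4.78% | 7.12% | 2.50 to 4.85 |
| 20 | 6.68% | 10.57% | 13.57% | 3.88 to 6.89 |

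If half of all subjects came from pimavanserin (also an assumption), the gap in the all-subjects column is half as large, about 0.2 to 3.4 points. For t = 60 ms the largest case is s = 20: 0.14% for m = 0, 0.30% for m = 5 and 0.47% for m = 8. The Table 5 change criterion is therefore hardly touched.

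Two things are left out. The overall post-baseline maximum takes the worst of several visits, so its rates would be higher than those at a single visit. Exclusion criterion 2 (Protocol 4.2) removes subjects whose QTcF is already high at the on-drug Baseline. Some of those would have had large double-blind increases, so this would tend to narrow the gap.

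**3. What does the SAP give on its narrowest reading?**

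- QTc change from the antecedent Baseline, by visit and antecedent treatment group, with mean, SE, SD, median, minimum and maximum (SAP 5.1 and Section 14). The maximum shows whether anyone rose by more than 30 or 60 ms at that visit. The formula above needs only a mean and an SD, so the share can be approximated.
- Observed QTcF categories up to above 500 ms, which need no Baseline.
- Change categories for prior-placebo subjects, whose open-label Baseline is free of pimavanserin.

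The one thing not guaranteed is the exact number of prior-pimavanserin subjects above 30 ms from their pre-drug value. The antecedent values needed for it must already be in the analysis data, because the exploratory change analysis uses them.

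**The case for a change.** The best argument for a change is the responder rate. It is a continuous score turned into a yes/no by the size of its change, just as the QTcF categories are, and the authors still wrote it a sentence of its own. A programmer who reads strictly could infer that categorised changes without such a sentence use the open-label Baseline only. One added sentence would cost little. This stands as evidence that the text is not explicit. It also stands that a mean, an SD and a maximum are not a count.

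The other textual points are weaker. The convention in SAP 5.1 governs how categories are displayed and is silent on Baselines. Protocol 9.5.3.2 cannot settle the matter, because the protocol has only one Baseline and the two-Baseline scheme appears only in the SAP. The lipid and glucose criteria are moves between classes, so a rule about change in a continuous measure would not have reached them. That leaves responder rate, a named efficacy endpoint, as the single true parallel.

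There is also a pointer the other way. SAP 14.3 lists vital-sign records "for which at least one PCI value (including Baseline) was observed". Every criterion in Table 4 needs a change, so a Baseline value can qualify only against an earlier reference. That is a hint, not proof, but it suggests that the authors did not confine change criteria to the open-label Baseline.

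**Conclusion.** No change to the plan is needed. SAP 14.4 leaves a detail open, but Section 14 supplies a natural answer: QTcF is a continuous ECG measure, its change is to be shown from both Baselines, and the categories are another display of that change. SAP Section 1 puts table layouts in a separate document, which is not available here. That is the usual place to settle such a point.

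Under the assumptions above, the narrow reading would lower the above-30 ms share in prior-pimavanserin subjects by 0.5 to 6.9 points at one visit, and would barely move the above-60 ms share. Most of that range comes from the assumed SD. The study is descriptive with no hypothesis tests. QTc means and extremes from both Baselines, the observed categories and the prior-placebo column would all still be reported, so the QT conclusions would remain sound. Extending the request to Table 5, to the weight criterion in Table 4 or to the listings would gain almost nothing: the above-60 ms rates are tiny, and no bias has been shown for weight.

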## 4.2 Exclusion Criteria

A subject must meet none of the following exclusion criteria to be eligible for the study.

1. Is judged by the Investigator or the Medical Monitor to be inappropriate for the study, due to AEs, medical condition, or noncompliance with investigational product or study procedures in Study ACP-103-054 or Study ACP-103-059, or is judged to be a danger to self or others
2. Has any of the following electrocardiogram (ECG) results at Baseline (i.e., Week 6/ EOT visit of Study ACP-103-054 or Study ACP-103-059):
  - a. If the subject is **not** on citalopram, escitalopram, or venlafaxine (immediate or extended release):
    - i. QTcF >450 ms, if QRS duration <120 ms
    - ii. QTcF >470 ms, if QRS duration  $\geq$ 120 ms
  - b. If the subject is on citalopram, escitalopram, or venlafaxine (immediate or extended release):
    - i. QTcF >425 ms, if QRS duration <120 ms
    - ii. QTcF >450 ms, if QRS duration  $\geq$ 120 ms
3. Has a heart rate (as measured by peripheral pulse rate) <50 beats per minute at Baseline (i.e., the Week 6/EOT visit of Study ACP-103-054 or Study ACP-103-059) not explained by regular exercise or medication, in discussion with the Medical Monitor

4. Has a body mass index (BMI)  $<18.5 \text{ kg/m}^2$  or known unintentional clinically significant weight change (i.e.,  $\pm \geq 7\%$  of body weight) in Study ACP-103-054 or Study ACP-103-059 as assessed by the Investigator
5. Has clinically significant laboratory abnormalities that, in the judgment of the Investigator or Medical Monitor, would either:
  - a. jeopardize the safe participation of the subject in the study; OR
  - b. would interfere with the conduct or interpretation of safety or efficacy evaluations in the study
6. Is suicidal as defined below at Visit 1 (Baseline) of the present study:
  - a. An answer of “yes” to C-SSRS questions 4 or 5 (current or over the last 6 months); OR
  - b. Has attempted suicide within 1 year prior to Visit 1 (Baseline); OR
  - c. Is actively suicidal in the Investigator’s judgment
7. Has developed delirium or a neurologic, cardiovascular, respiratory, gastrointestinal, renal, hepatic, hematologic, or other medical or mental disorder, including cancer or malignancies that, in the judgment of the Investigator or the Medical Monitor, would increase the risk associated with taking study medication or significantly interfere with the conduct or interpretation of the study

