Number and percentage of subjects with potentially clinically important (PCI) laboratory values at scheduled post-Baseline visits and overall post-Baseline will be summarized by Baseline status (all or within normal range) for selected parameters. PCI criteria are listed in [Table 2](#) and [Table 3](#). For the overall post-Baseline summaries, all post-Baseline values will be considered, including unscheduled and out of window values. Subjects with multiple PCI values for a given parameter will be counted only once for that parameter. For the by-visit summary, the numerator for the percentage is the number of subjects with a post-Baseline PCI value for the given parameter and visit, and the denominator is the number of subjects with non-missing values for the given parameter and visit. For the overall post-Baseline summary, the numerator for the percentage is the number of subjects with at least 1 post-Baseline PCI value for the given parameter, and the denominator is the number of subjects with at least 1 post-Baseline value for the given parameter. For hemoglobin, hematocrit, and uric acid, the count and percentage of subjects with PCI values will be presented for each gender as well as for both genders combined. A listing of all PCI values in study ACP-103-055 will be provided. This listing will include all observations from study ACP-103-055 for those subjects and parameters for which at least one PCI value (including OL Baseline) was observed.

Table 2 Criteria for Potentially Clinically Important Laboratory Values – Hematology and Chemistry

Analyte	Conventional Unit	Low PCI Criteria	High PCI Criteria	SI Unit	Low PCI Criteria	High PCI Criteria
Hematology (whole blood)						
Hemoglobin (male)	g/dL	<11	>18	g/L	<110	>180
Hemoglobin (female)	g/dL	<10	>17	g/L	<100	>170
Hematocrit (male)	%	<30	>55	L/L	<0.3	>0.55
Hematocrit (female)	%	<30	>50	L/L	<0.3	>0.5
Leukocyte (White Blood Cell Count)	x 10 ³ /uL	≤2.8	≥15	x 10 ⁹ /L	≤2.8	≥15
Neutrophils	x 10 ³ /uL	≤1.5	No upper limit	x 10 ⁹ /L	≤1.5	No upper limit
Platelet Count	x 10 ³ /uL	≤75	≥700	10 ⁹ /L	≤75	≥700
Chemistry (serum or plasma)						
ALT (SGPT)	U/L	No lower limit	≥3 X ULN	U/L	No lower limit	≥3 X ULN
AST (SGOT)	U/L	No lower limit	≥3 X ULN	U/L	No lower limit	≥3 X ULN
Total Bilirubin	mg/dL	No lower limit	≥1.5 ULN	umol/L	No lower limit	≥1.5 ULN
BUN	mg/dL	No lower limit	≥30.0	mmol/L	No lower limit	≥10.71
Creatine Kinase (CK)	U/L	No lower limit	≥3 ULN	U/L	No lower limit	≥3 ULN

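### The QRS and PR counts of potentially clinically important ECG values ignore Baseline, so no planned table shows how many subjects newly crossed the limits

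*SAP*

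**What the plan says.** SAP 14.4 states that "Electrocardiogram values will be considered PCI if they meet or exceed the upper limit values listed in Table 5". For QRS and PR, Table 5 gives an absolute limit only: 120 msec or more and 220 msec or more. The only row that uses change from Baseline is the one for QTc (more than 60 msec).

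When all visits are taken together, the count is defined thus: "the numerator for the percentage is the number of subjects with at least 1 post-Baseline PCI value for the given parameter". The base of the percentage is equally free of any Baseline condition: "the denominator is the number of subjects with at least 1 post-Baseline value for the given parameter". The by-visit percentages are built the same way.

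Protocol 4.2, exclusion 2, opens with "Has any of the following electrocardiogram (ECG) results at Baseline" and then lists QTcF limits that depend on QRS. Subjects not on citalopram, escitalopram or venlafaxine are excluded under "ii. QTcF >470 ms, if QRS duration" of 120 ms or more; those on one of these drugs are excluded under "ii. QTcF >450 ms, if QRS duration" of 120 ms or more. Wide QRS alone is not an exclusion. No PR limit appears in the ECG exclusion.

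The SAP uses Baseline in its other PCI summaries. Laboratory PCI values "will be summarized by Baseline status (all or within normal range) for selected parameters" (SAP 14.2). In SAP 14.3, Table 4, PCI blood pressure and pulse need both an extreme value and a change from Baseline, and PCI weight is defined by change alone.

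**The concern.** A subject who enters with QRS of 120 ms or more meets the PCI criterion before the first open-label dose. If the value stays there, the subject is counted as a post-Baseline PCI case although nothing has changed. The same can happen for PR, since nothing in the ECG exclusion keeps out a long PR interval.

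The percentage is then part prevalence at entry and part new onset, in unknown proportions. It can mislead both ways: a figure made up mostly of entry values may look like a signal, and a few new cases may be lost among old ones. Every subject receives pimavanserin, so there is no concurrent control arm against which to judge the figure. Summaries by antecedent treatment do not supply one.

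**Working it through.** The plan states no figure for this point, so there is nothing to reproduce. The check has two parts.

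**1. Do other planned outputs give the count of new crossings?**

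- *Change from Baseline in PR and QRS by visit (SAP 14.4).* These are descriptive statistics of a continuous measure. They do not count subjects who cross a limit.
- *Shift table of the cardiologist's interpretation (SAP 14.4).* It covers normal or abnormal for the whole ECG. It does not isolate QRS or PR, and a subject already abnormal at Baseline cannot show a new crossing in it.
- *QTcF categories (SAP 14.4).* They do not cover QRS or PR.
- *PCI listing (SAP 14.4).* It shows all observations in this study for each flagged subject and parameter, open-label Baseline included. New crossings can be picked out by hand, but they are not tabulated.

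So no planned table gives the count.

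**2. How large could the mixing be?**

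Inputs:
- b, the share at or above the limit at Baseline. The documents do not give it; assumed range 0.5% to 3%.
- i, new onset among the rest. The documents do not give it; assumed range 0.5% to 1%.
- Persistence: every subject in b is assumed to have at least one post-Baseline value at or above the limit. One reading among up to eight scheduled post-Baseline ECGs (Weeks 2, 4, 8, 12, 16, 28, 40 and 52) is enough.
- N = 420 (SAP 3.5), for scale only. The same section says the number will be lower.

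Formulas:
- Reported proportion = b + (1 − b) × i
- Pre-existing share of the reported count = b / [b + (1 − b) × i]

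| b | i | Reported | Pre-existing share |
|---|---|---|---|
| 0.5% | 0.5% | 1.00% | 50% |
| 0.5% | 1% | 1.49% | 33% |
| 1% | 0.5% | 1.49% | 67% |
| 1% | 1% | 1.99% | 50% |
| 2% | 0.5% | 2.49% | 80% |
| 2% | 1% | 2.98% | 67% |
| 3% | 0.5% | 3.49% | 86% |
| 3% | 1% | 3.97% | 76% |

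The two ends written out:
- Low: 0.005 / (0.005 + 0.995 × 0.01) = 0.005 / 0.01495 = 33%.
- High: 0.03 / (0.03 + 0.97 × 0.005) = 0.03 / 0.03485 = 86%.

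At N = 420 the high case is 12.6 subjects with entry values plus 2.0 new ones, 14.6 in all. The low case is 2.1 plus 4.2, 6.3 in all. N cancels from the share, so early stopping does not change it. If b = 0 the share is 0%; if b is above zero and i = 0 it is 100%.

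**The case against.** The SAP breaks no promise of its own. It calls these values post-Baseline PCI and never treatment-emergent, and a QRS of 120 msec measured after Baseline is exactly that. The listing shows the Baseline value of every flagged subject. At the assumed rates and N = 420 there would be about 4 to 17 such subjects (1.00% and 3.97% of 420), so sorting them by hand is quick. The study is descriptive, and QRS and PR PCI values are neither the primary endpoint nor a listed exploratory endpoint. The ECG effect that the protocol describes is QT prolongation, for which Table 5 and the QTcF categories do use change from Baseline. All of this stands, and it keeps the weight low. It does not supply the missing table.

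Three stronger readings are tempting, and the documents do not support them.

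- *The plan cannot show whether conduction abnormalities emerged.* The listing can show it, and the change summaries and shift table bear on it indirectly. What is missing is a tabulated count.
- *Most of the reported count will be pre-existing.* That depends on assumed rates and on persistence. Being eligible does not mean that any such subject enrolled, and the entry criteria of the antecedent studies are not in these documents. For PR the evidence is thinner than for QRS: it is only that no limit is listed.
- *Subjects below the limit at open-label Baseline who later cross it are the treatment-emergent cases.* Open-label Baseline is the end-of-treatment visit of the antecedent study (Protocol 3.1), and some subjects had received pimavanserin there (SAP 10.1.2). A change that arose on double-blind pimavanserin would be classed as already present.

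**Conclusion.** The point holds as a reporting weakness of minor weight. The QRS and PR PCI percentages do not separate values present at entry from new ones, and no planned table does so. For QRS this follows directly from setting SAP 14.4 beside exclusion 2; for PR it follows from the absence of a listed limit.

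The size cannot be known from the documents. The 33–86% range is an illustration resting on assumed prevalence, assumed onset and full persistence. No hypothesis test is affected.

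**What to change.** In SAP 14.4, add that QRS and PR PCI counts and percentages will be presented for all subjects and for subjects not meeting the criterion at Baseline, the latter over subjects who were below the limit at Baseline and have a post-Baseline value. This follows the spirit of the laboratory split in SAP 14.2 but is not identical to it: that split uses the normal range, and here the PCI limit itself is the dividing line.

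Do it against two Baselines, extending the convention in SAP 5.1:
- open-label Baseline, labelled *new since open-label Baseline* and not treatment-emergent;
- antecedent-study Baseline, because some subjects were already on pimavanserin at open-label Baseline.

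In both cases the post-Baseline values remain those of Study ACP-103-055. The cost is a sentence or two in the SAP and one extra column set. No new data are needed: the Baseline ECG is in the schedule, and SAP 14 already plans ECG changes from both Baselines.
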